### **5.2.2 Waiver of Documentation of Consent (Implied consent, Verbal consent, etc.)**

Adults with Major Depression

Given the minimal risk nature of the intervention we will, as in past studies of PlayFit, use a Summary Explanation of Research document to consent participants. The highest risk part of the PlayFit RCT, the maximal fitness test, will not be performed in the Feasibility Studies, reducing risk significantly. Effort level will slowly be increased (by increasing the duration of play periods) over the first 4-6 weeks to accommodate for low levels of fitness at baseline.

## **5.3 Consent – Other Considerations**

### **5.3.1 Non-English Speaking Subjects**

Not applicable.

### **5.3.2 Cognitively Impaired Adults**

Not applicable.

#### **5.3.2.1 Capability of Providing Consent**

Subjects must be able to answer all questions during the phone screener. Those who cannot answer screener questions clearly and reliably will be assumed to be incapable of providing consent.

#### **5.3.2.2 Adults Unable To Consent**

Not applicable. We will only be enrolling subjects who can provide their own consent.

#### **5.3.2.3 Assent of Adults Unable to Consent**

Not applicable. We will only be enrolling subjects who can provide their own

consent.

### 5.3.3 Subjects who are not yet adults (infants, children, teenagers)

#### 5.3.3.1 Parental Permission

For the Adolescent Feasibility project only, parental consent is required, as subjects will be ages 10-12 and in the 6th or 7th grade.

#### 5.3.3.2 Assent of subjects who are not yet adults

For the Adolescent Feasibility project only, participants (ages 10-12 and in the 6th or 7th grade) will be required to provide assent. In all other projects, this will be not applicable as we will be only enrolling adults.

## 6.0 HIPAA Research Authorization and/or Waiver or Alteration of Authorization

### 6.1 Authorization and/or Waiver or Alteration of Authorization for the Uses and Disclosures of

#### PHI Check all that apply:

- Not applicable, no identifiable protected health information (PHI) is accessed, used or disclosed in this study. *[Mark all parts of sections 6.2 and 6.3 as not applicable]*
- Authorization will be obtained and documented as part of the consent process. *[If this is the only box checked, mark sections 6.2 and 6.3 as not applicable]*
- Partial waiver is requested for recruitment purposes only (Check this box if patients' medical records will be accessed to determine eligibility before consent/authorization has been obtained). *[Complete all parts of sections 6.2 and 6.3]*
- Full waiver is requested for entire research study (e.g., medical record review studies). *[Complete all parts of sections 6.2 and 6.3]*
- Alteration is requested to waive requirement for written documentation of authorization (verbal authorization will be obtained). *[Complete all parts of sections 6.2 and 6.3]*

### 6.2 Waiver or Alteration of Authorization for the Uses and Disclosures of PHI

#### 6.2.1 Access, use or disclosure of PHI representing no more than a minimal risk to the privacy of the individual

##### 6.2.1.1 Plan to protect PHI from improper use or disclosure

Information is included in the "Confidentiality, Privacy and Data Management" section of this protocol.

##### 6.2.1.2 Plan to destroy identifiers or a justification for retaining identifiers

Identifiers will be kept until all data is analyzed

#### 6.2.2 Explanation for why the research could not practicably be conducted without access to and use of PHI

Clinic directors for the Departments of Family and Community Medicine and Medicine will create lists of patients who meet the age cutoff (Ages 10-12 and in the 6th or 7th grade for Adolescent Feasibility project and ages 18 and over for other parts of the project) in the desired geographic area. They will provide us names and mailing address so research staff can send recruitment letters. We need to collect personal health information from the participants during the phone screening to determine eligibility for the study.

### **6.2.3 Explanation for why the research could not practicably be conducted without the waiver or alteration of authorization**

Since this is an exercise study we want approval from the participant's primary care provider to minimize any health risks. We will ask their Primary Care Provider to provide permission to participate, if their answers on the screener, about their symptoms and past medical history, suggest that physical activity may harm them.

### **6.3 Waiver or alteration of authorization statements of agreement**

Protected health information obtained as part of this research will not be reused or disclosed to any other person or entity, except as required by law, for authorized oversight of the research study, or for other permitted uses and disclosures according to federal regulations.

The research team will collect only information essential to the study and in accord with the 'Minimum Necessary' standard (information reasonably necessary to accomplish the objectives of the research) per federal regulations.

Access to the information will be limited, to the greatest extent possible, within the research team. All disclosures or releases of identifiable information granted under this waiver will be accounted for and documented.

## **7.0 Study Design and Procedures**

### **7.1 Study Design**

RCT

We propose a 12-month randomized trial to answer the following question for both patients, health care providers and fitness center directors: "What group exercise program will best promote long-term adherence and fitness?" The design consists of two activity conditions (Group Fitness, PlayFit). We hypothesize that, by enhancing perceived enjoyment and thereby attendance and adherence, PlayFit will lead to greater gains in fitness, and better physical and mental health than a traditional Group Fitness program [77, 78].

Eligible subjects will be randomly assigned to two exercise conditions, group fitness and PlayFit. They will then be offered up to 4 scheduled sessions of each exercise program per week. They will complete fitness testing and baseline, 6 and 12 months. We hypothesize that subjects in the PlayFit condition will experience greater gains in fitness (measured by V02max) and that this will be due to the higher levels of satisfaction with PlayFit, which will lead to greater levels of attendance and thereby, fitness.

Of note, each participant can, if they choose, have one additional person from their household join the project and participate in the intervention but not in the fitness testing or measures at baseline, 6-, and 12-months. This is designed to reduce nonadherence and to increase enrollment as many people join fitness programs with a household contact and randomizing them to different conditions is impractical. These individuals are referred to in this protocol as a "HOUSEHOLD MEMBER" to denote their different level of involvement.

#### **RCT: COVID-19 Design Modifications**

[figure not shown]
We have implemented modifications to the PlayFit study and the operations of delivering the in-person interventions to adhere to the safety guidelines and considerations outlined by Penn State University, federal, state, and local governments, the CDC, and Pennsylvania DOH, to help our team prepare for a reality in which many of the COVID-related mandates may remain for the foreseeable future. The research design modifications we propose aim to: 1) examine the feasibility of applying the recommended social distancing measures to the already typically socially distanced PlayFit sport-games (i.e., designed to be non-contact, with passes being made between distanced individuals); and 2) test the impact of applying

health and safety protocol measures to the delivery of the in-person interventions.

In the event of a prolonged exercise session cancellation period due to either a disease outbreak or Penn State University recommendation to stop all exercise sessions, study staff will contact all previously-enrolled participants (pre-cancellation period) via a study-wide email and request they contact research staff via email or phone call if willing to continue participating in the exercise sessions upon the study's restart. Study staff will individually follow-up with participants who indicate an interest in continuing via email or phone call to coordinate a phone call to discuss the continuation and answer any questions the participant may have. If interested, participants will be re-invited to the exercise sessions.

As result of an unforeseen, COVID-19-related, prolonged exercise intervention cancellation (occurring between the dates of January 10, 2022 and February 21, 2022, following Penn State University mandates to pause all in-person human subjects research) and halt in the normal delivery of the exercise intervention sessions (occurring between the dates of February 21, 2022 and April 4, 2022, in an effort to recondition subjects to the exercise interventions and mitigate the risk of injuries), participants among the 2021 cohort may be requested to continue his or her study participation beyond the 12-month time point, to achieve six (6) continuous months of normal exercise intervention delivery between the months of February 2022 and August 2022. As result of the aforementioned effects of the COVID-19 pandemic, the study will treat this 6-month period as an individual 6-month study entity, completing the listed 9- and 12-month measurements (7.2 Study Procedures, RCT) with subjects at the 3- and 6-month post-resumption of the normal delivery of exercise intervention time points, respectively.

Participants among the 2019 cohort enrolled in the trial between the months of June and December 2019. Exercise intervention-related activities began in the month of September 2019 and continued through February 2020, prior to being halted as result of the onset of the COVID-19 pandemic. 6-month study visits occurred between the months of December 2020 and February 2020, prior to being halted as result of the onset of the COVID-19 pandemic. 12-month study visits did not occur among participants in the 2019 cohort, as result of the prolonged, COVID-19-related suspension of in-person human subjects research.

Participants among the 2021 cohort primarily enrolled in the trial between the months of June and October 2021. Exercise intervention-related activities began in the month of July 2021 (among subjects first to enroll in the study) and continued through December 2021, prior to being halted as result of the COVID-19 case count surge and subsequent College of Medicine (COM) mandate to pause all in-person human subjects research. The aforementioned in-person human subjects research pause rendered the 6-month study visits not feasible (due to COM mandates), disrupting data collection activities considerably. Following a 3-month halt in the normal delivery of the exercise intervention sessions between the dates of

January 10, 2022 and April 4, 2022, as outlined above, exercise interventions continued; the normal delivery of exercise intervention sessions is set to continue through September 2022, allowing participants among the 2021 cohort to achieve six (6) continuous months of exercise intervention participation, with modified 12-month study visit procedures to occur at the conclusion of the aforementioned 6-month time period.

### RCT: COVID-19 Risk Mitigation

Research study staff will instruct participants to park their vehicle in the designated Visitor Parking area(s) of the recreational space/facility. Participants will be instructed to walk from the parking area(s) to the pre-participation check-in station. All participants must bring their own water bottles and/or drinks to the project site; traditional sport hydration methods (e.g., shared water cooler) will not be provided. All participants will wear their own appropriate workout clothing, and athletic apparel shall not be shared.

Research study staff members and study participants will be required to don face masks at all times and maintain a 6-foot distance from one another at all times. At least one research study staff member will be present on-site during all project operations. Research study staff members will assume responsibility for ensuring only research staff and participant personnel are present on-site; non-participant attendance policies will be outlined with the participants in advance of the scheduled sessions. Up to a total of 30 research participants may be present at the site during each exercise session. Upon participant arrival at the project site, research study staff will require all research participants to complete a pre-participation health screening questionnaire and a temperature assessment using a touchless thermometer. Participants reporting new symptoms or with temperatures  $\geq 100.4$  degrees Fahrenheit will not be permitted to participate. Research study staff will configure the space of the check-in, health screening location, via the use of visual aids (e.g., field markers), to ensure a 6-foot distance between participants is maintained at all times.

During the exercise sessions, participants will be asked to wear a mask and adhere to the socially-distanced rulesets developed by research study staff. We have developed modified rulesets (maintain 6-feet from the player with the ball/Frisbee being defended in PlayFit, for example) to create both a socially-distanced field of play/exercise space and a socially-distanced rest area/sideline using various visual aids (e.g., field markers; designated rest areas). During the rest intervals between periods of exercise, participants will be asked to remain within his/her designated rest area. Participants will be provided his/her designated rest area after having successfully passed the pre-participation screening process. Throughout the exercise session, study staff will space themselves appropriately in an effort to conduct ongoing quality control examinations of the modified intervention, ensure masks are worn and the 6-foot ruleset protocol is adhered to as outlined, and to ensure the social distancing measures set forth in this application between study staff members are maintained at all times.

Hand sanitizer units with at least 60% alcohol will be made available for participants and research study staff. Research study staff will request participants use hand sanitizing solution upon arrival to the site and prior to touching any of the sport-game implements/exercise equipment. Whenever possible, sport-game implements/exercise equipment and other personal items shall be separated and not shared. Shared implements used to conduct the active sport-game/exercise session shall be properly disinfected between periods of activity. Research study staff have set forth a schedule for routine cleaning and disinfection. The schedule will include at minimum the cleaning of all equipment and game implements both upon arrival on-site and following the exercise session.

#### Feasibility – Adolescent, Major Depressive

The feasibility study is designed in two phases, among two separate populations (adolescents age 10-12 and in the 6th or 7th grade, adults being treated for major depressive disorder). First, we will conduct focus groups among adults to identify changes to the PlayFit intervention that will be needed to adapt it to the target population. Second, we will conduct a 2-month single-group study among 50 members of each group to understand the rate of attendance and whether exposure to PlayFit increases the level of physical activity (using an activity monitor worn at baseline, and monthly for 2 months) and perceived enjoyment from physical activity.

#### Feasibility – Older Adult

The feasibility study is designed in two phases, among adults 51-70. First, we will conduct focus groups among adults to identify changes to the PlayFit intervention that will be needed to adapt it to the target population. Second, we will conduct a 3-month single-group study among 50 members to understand the rate of attendance and whether exposure to PlayFit increases fitness (measured by V02 at the baseline and 12-week time points) as well as the level of physical activity (using an activity monitor worn at baseline and the 12-week time point) and perceived enjoyment from physical activity.

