### 1.2 Primary Study

#### Endpoints RCT ONLY:

**Aerobic Fitness (VO2max).** Aerobic fitness will be assessed using a single maximal graded treadmill test, using a Bruce protocol and ECG or heart rate monitoring [1] using a metabolic measurement system such as a COSMED K5, Parvomedics or other system. The test will be terminated at a point of volitional fatigue, to ensure true VO2Max is achieved. Breath-by-breath VO2 is determine for each 3-minute stage

of the Bruce protocol. Three-minute stages ensure steady-state VO2 consumption (work output) has been achieved.

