**Blood Pressure.** Blood pressure will be assessed according to the recommendations of the American Heart Association [14]. Resting blood pressure will be measured with the participant in a seated position using a professional, calibrated, aneroid sphygmomanometer. The average of three blood pressure measurements will be recorded, as our team has done in other studies [15].

**5X Sit-to-Stand.** The 5X Sit-to-Stand (5XSTS) will be administered by research study personnel at both the baseline and 12-week time points in the Older Adult Feasibility Study. Study subjects will be requested to perform the 5XSTS test as a measure of functional lower extremity strength.

**Berg Balance Scale.** The Berg Balance Scale (BBS) will be administered by research study personnel at both the baseline and 12-week time points in the Older Adult Feasibility Study. Study subjects will be requested to perform the 14-item BBS test as a measure of static balance and fall risk among older adults.

**3-Minute Step Test.** The YMCA 3-Minute Step Test (3MST) will be administered by research study personnel at both the baseline and 12-week time points in the Older Adult Feasibility Study. Study subjects will be requested to perform the test as a measure of cardiorespiratory fitness among older adults.

**Physical Function.** The 4-item, PROMIS Physical Function Questionnaire will be administered via automated, online REDCap online survey at both the baseline and 12-week time points in the Older Adult Feasibility Study.

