with a backrest as well as a standard height step, as a measure of balance and physical function. The balance assessment will require study subjects to transfer from a seated to a standing position, using several variations of transfer (Berg Balance Scale); subjects will also perform additional, functional balance activities (Berg Balance Scale). Subjects will be instructed on how to complete the test prior to administration. The test will be stopped when completion all fourteen (14) balance items is achieved, unless limited by symptoms.

Subjects will complete a submaximal test using a stepping tool, using an ECG or heart rate monitoring [1] metabolic measurement system, such as a COSMED, Parvomedics or other system. Each subject will be hooked up to mask that will collect their expired gases. They will also be connected to the Quinton Q-Stress ECG machine to monitor heart rhythms or they will wear a polar heart rate monitor. Each test will require the study subjects to step up-and-down a step for a total of 3-minutes; subjects will be instructed on how to complete the test prior to administration. They will also be instructed on how to use the Borg Rated of Perceived Exertion (RPE) scale (6-20). The test will be stopped when a total of 3-minutes is achieved, unless limited by symptoms.

Clinical staff are present to both perform and supervise the individuals, to ensure safety. Testing will be overseen by [name], exercise physiologist and Lab Director.

During this visit, subjects will be provided with explanation about how and when to wear the accelerometer. They will be asked to wear it while awake for 7 days, rather than just when they are active. They will be shown how to wear it, on the waist, so that it captures movement appropriately. Participants will be emailed or called after 48-96 hours to be sure they are wearing it and help troubleshoot in case of difficulty with the monitor.

Research coordinator will provide payment to subjects among the Older Adult Feasibility study for completing the baseline visit following receipt of the accelerometer.

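### Older-adult fitness gain is to be measured by VO2 on a repeated submaximal 3-minute step test, where VO2 mainly reflects the work done and is a poor index of fitness

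*Combined protocol and SAP*

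**What the plan says.** Section 7.1 (Feasibility – Older Adult) sets a question with a direction, "whether exposure to PlayFit increases fitness", and names VO2, not VO2max, as the measure at baseline and week 12.

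Section 7.2.6 (Feasibility Studies: Older Adults) describes the test: "Subjects will complete a submaximal test using a stepping tool". Gas is collected: "Each subject will be hooked up to mask that will collect their expired gases". Heart rate is followed by ECG or a heart rate monitor, and participants are taught the Borg exertion scale. The end point is a set time: "The test will be stopped when a total of 3-minutes is achieved, unless limited by symptoms". There is no graded increase and no criterion of maximal effort. Section 7.2.15 repeats the test at 12 weeks under the same protocol as at baseline.

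Section 1.3 lists the YMCA 3-Minute Step Test and gives its purpose: "Study subjects will be requested to perform the test as a measure of cardiorespiratory fitness among older adults". It names no score. The Older Adult measurement table in Section 7.2 lists aerobic fitness among the secondary outcomes, again without a score. Section 5.2.2 says that the maximal fitness test is not done in the feasibility studies.

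**The concern.** Oxygen uptake tells us about capacity when the participant is pushed to a maximum. At a set submaximal load it tells us mainly what that load costs. The Older Adult study drops the maximal test used in the RCT but keeps VO2 as its measure of fitness.

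If the load is the same at both visits, a fitter participant does the same stepping for about the same oxygen uptake, at a smaller share of a higher maximum. Raw VO2 does not show that share. A programme that worked could therefore look as if it had done nothing, and a flat result could be misread as evidence that PlayFit does not improve fitness in older adults. Gas would have been collected at two laboratory visits per participant for a number that does not answer the question in Section 7.1.

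**Working it through.** The plan gives no effect size, SD, power or sample size for step-test VO2, so there is no stated figure to reproduce. The check sets the sections side by side and then applies a simple model.

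**Sections compared**

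- RCT (Section 1.2): a graded treadmill test to volitional fatigue, so that VO2max is reached.
- Older Adult study (Section 7.2.6): "Each test will require the study subjects to step up-and-down a step for a total of 3-minutes". The load is not raised and the participant is not taken to a maximum.
- Step height and cadence appear nowhere. That the load is equal at the two visits is an inference from the named test, the set duration and the repeat of the same protocol.
- No section says that VO2max is to be estimated from VO2 and heart rate, or that heart rate during or after stepping is the score.
- In the RCT endpoint text, Section 1.2 says that 3-minute stages ensure that steady-state VO2 "consumption (work output) has been achieved". This describes treadmill stages, so it is context only. The argument rests on the step test's design.

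**Model**

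Below maximum, steady-state VO2 = c × W, where c is the oxygen cost per unit of work and W is the work rate. VO2max is not in the formula. If W is equal at both visits, the change in VO2 is W × (change in c). Relative effort is VO2 / VO2max.

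**Assumed inputs (none is in the documents)**

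Baseline VO2max 25 to 35 ml/kg/min, step-test VO2 18 to 22 ml/kg/min, true gain in VO2max 10%, and oxygen cost unchanged or lower by 3% or 5%.

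| VO2max before → after | Step-test VO2 at baseline | Change, cost unchanged | Change, cost −3% | Change, cost −5% | Relative effort before → after (cost unchanged) |
|---|---|---|---|---|---|
| 25 → 27.5 | 22 | 0.0 | −0.66 | −1.10 | 88.0% → 80.0% |
| 30 → 33 | 20 | 0.0 | −0.60 | −1.00 | 66.7% → 60.6% |
| 35 → 38.5 | 18 | 0.0 | −0.54 | −0.90 | 51.4% → 46.8% |

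For the middle row: 20 × 0.97 = 19.4, a change of −0.6; 20 × 0.95 = 19.0, a change of −1.0; 20/30 = 66.7% and 20/33 = 60.6%. Fitness rises by 10% in every row, yet VO2 stays level or falls slightly. Only relative effort moves.

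**Body weight**

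If W is proportional to body mass, a 3% weight loss lowers absolute VO2 (L/min) by 3%. Per kg, VO2 and mass fall together: 0.97 / 0.97 = 1, so nothing changes. Section 7.1 does not state the unit.

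**The case against.** Several objections have force.

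- **The test need not last 3 minutes for everyone.** It can stop early for symptoms. Among sedentary adults aged 51 to 70, some may stop early at baseline and go further at 12 weeks, or may work near their maximum. VO2 could then move with fitness. This stands, and it limits the point to those who complete the 3 minutes below their maximum.
- **Equal load is inferred.** Only the duration is fixed in the text. If pace were free, VO2 could rise because the participant stepped faster. This also stands as a condition, but a rise of that kind would show more work done and would be no cleaner a measure of fitness.
- **VO2 may be shorthand for an estimated maximum.** Gas, heart rate and perceived exertion are gathered in the same test, and Section 7.1 does not literally say that raw VO2 must rise. But no section describes such an estimate, and a fitness increase measured by VO2 is most naturally read as a rise in VO2.
- **The consequence is small.** Accelerometry is the main outcome, Aim 3's hypotheses concern MVPA and the association of enjoyment with attendance, and the sample size in Section 8.1 rests on MVPA. This is right and bears on priority.

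Two stronger readings are tempting. A reader might infer that VO2 can never show a fitness gain here. The early-stopping rule and the unstated step height and cadence do not support that. A reader might also infer that VO2 will fall in people who lose weight. As shown above, that holds only for absolute VO2, and the VO2max figures in Section 8.2 (26.5 rising to 32.6, no unit printed) are of a size that suggests values per kg.

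**Conclusion.** The point holds in limited form. As written, the plan uses raw submaximal VO2 to look for a fitness increase, and that is a poor index. Among participants who complete the 3 minutes below their maximum, at equal step height and cadence, the expected change in VO2 after a true gain is about zero. It becomes a fall of roughly 0.5 to 1.1 ml/kg/min if stepping economy improves by 3% to 5%. These sizes are illustrations on assumed values; the direction follows from the test design.

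The effect is confined to a secondary outcome in a single-group study of up to 50 people. The RCT's VO2max endpoint comes from a different, maximal test and is not affected. The change should be made, but the Older Adult study's main outcome does not depend on it.

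**What to change.** Amend Section 1.3 (3-Minute Step Test), Section 7.1 (Feasibility – Older Adult), the Older Adult table in Section 7.2 and the test description in Section 7.2.6 so that they agree on the following:

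1. The fitness readout is heart rate at the end of the 3-minute test, with a lower value meaning fitter.
2. That value is recorded as study data at both visits. The present text describes monitoring but does not say that an end-of-test value is kept.
3. Step height and cadence are stated and are the same at both visits. Without this, heart rate is no more interpretable than VO2.
4. VO2 is kept as a check that the workload was equal at the two visits, with its unit stated.
5. Participants who stop before 3 minutes are reported separately.

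The cost is a wording amendment, one recorded value per visit and a standardised step. Heart rate is already monitored, so no new procedure is needed. The drawback is that rate-altering medicines affect heart rate; the plan should note this as a limitation.
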